### Reporting to the FDA

It is the responsibility of the IND sponsor-investigator to comply with IND safety reporting as set forth in the Code of Federal Regulations, Section 312.32. This responsibility includes providing an annual IND report to the FDA. In addition:

- The FDA will be notified via [contact]) or fax ([name]) within 7 calendar days of any SAE that is associated with study treatment, is unexpected, and is fatal or life-threatening.
- The FDA will be notified via fax ([name]) or online submission (<http://www.fda.gov/downloads/AboutFDA/ReportsManualsForms/Forms/UCM048334.pdf>) with a MedWatch (3500A or 3500) within 15 calendar days of any SAE that is associated with the study treatment, unexpected, and serious but not fatal or life-threatening. This includes any previous SAEs that were not initially deemed reportable, but are later determined to meet the criteria for reporting (i.e. by the DSMC).

## **Appendix II**

### **Sample Data Collection Forms for $^{68}\text{Ga}$ -DOTATOC PET/CT**

Patient ID \_\_\_\_\_

University of Iowa Hospital

**Inclusion / Exclusion Ga-68 DOTATOC PET Protocol**(IMPACT TRIAL)**INCLUSION**

1. Y / N      Age  $\geq$  6 months
2. Y / N      Histologically diagnosed or suspected (pediatric only) neuroendocrine tumor or other tumor with probable somatostatin receptors subtype 2
3. Y / N      Karnofsky performance status or Lansky Play Scale status of  $\geq$  60 (or ECOG/WHO equivalent)
4. Y / N      Subject is male; or is a female who is either, surgically sterile (has had a documented bilateral oophorectomy and/or documented hysterectomy), postmenopausal (> 1 years without menses),  $\geq$ 60 years old, or of childbearing potential for whom a pregnancy test (with the results known prior to investigational product administration) is negative. A negative pregnancy test will be required for all female subjects with child bearing potential. If a false pregnancy test is suspected, e.g., perimenopausal condition, an obstetrician will be consulted to determine if she is/is not capable of becoming pregnant. Female must also be non-lactating.

**EXCLUSION**

1. Y / N      Subject weighs more than 400 pounds. (Subjects who weigh more than 400 pounds will not be able to fit inside the imaging machines.)
2. Y / N      Inability to lie still for the entire imaging time (due to cough, severe arthritis, etc.)
3. Y / N      Inability to complete the needed investigational and standard-of-care imaging examinations due to other reasons (severe claustrophobia, radiation phobia, etc.)
4. Y / N      Does the subject have any additional medical condition, serious intercurrent illness, or other extenuating circumstance that, in the opinion of the investigator, may significantly interfere with study compliance?
5. Y / N      Peptide receptor radionuclide therapy (PRRT) within 4 weeks of Ga-68 DOTATOC PET/CT scan
6. Y / N      Treatment with Sandostatin LAR within 4 weeks, SQ Octreotide within 12 hours, or Lanreotide injection within 8 weeks of Ga-68 DOTATOC PET/CT (+/- 5%)

\_\_\_\_\_  
Signature of screening MD\_\_\_\_\_  
Date

Patient ID \_\_\_\_\_

## Data Collection for Imaging Visit

### Subject Data (IMPACT TRIAL)

1) Limited Physical Exam:

Weight \_\_\_\_\_ Height \_\_\_\_\_ BP \_\_\_/\_\_\_ RR \_\_\_\_\_ P \_\_\_\_\_ Temp \_\_\_\_\_

a) HEENT (Circle or fill in blank): NORMAL OR \_\_\_\_\_

b) Chest (Circle or fill in blank): NORMAL OR \_\_\_\_\_

c) Cardiovascular(Circle or fill in blank): NORMAL OR \_\_\_\_\_

d) Abdomen (Circle or fill in blank): NORMAL OR \_\_\_\_\_

e) Integument (Circle or fill in blank): NORMAL OR \_\_\_\_\_

f) Musculoskeletal (Circle or fill in blank): NORMAL OR \_\_\_\_\_

g) Neurological (Circle or fill in blank): NORMAL OR \_\_\_\_\_

Investigator (Signature) \_\_\_\_\_ (Date) \_\_\_\_\_

Patient ID: \_\_\_\_\_

**Data Collection for Ga-DOTATOC PET/CT** (IMPACT TRIAL)

This page will be completed in the PET Center: Date \_\_\_\_\_

1) Pregnancy test (urine) required? Y / N Results \_\_\_\_\_

2) Ga-68 DOTATOC Dose: \_\_\_\_\_ mCi @ Injection Time \_\_\_\_\_: \_\_\_\_\_

3) Uptake period \_\_\_\_\_ min.

4) Vital Signs (supine) at PET Completion: P \_\_\_\_\_, BP \_\_\_\_\_/\_\_\_\_\_, RR \_\_\_\_\_ Temp \_\_\_\_\_ °C

5) Were any adverse events reported or observed since the Ga-DOTATOC injection?

No  Yes

If yes, provide a narrative of what the patient reported and/or what was observed.

---

---

---

---

---

---

---

Signature of PET staff: \_\_\_\_\_ Date / Time: \_\_\_\_\_

**Karnofsky/Lansky Performance Status**

This Karnofsky/Lansky performance status is used to determine the functional status of a subject. Performance status is a critical data field that has been determined to be essential for all outcome-based analyses. The Karnofsky Scale is designed for recipients aged 16 years and older, and the Lansky Scale is designed for recipients less than 16 years old. Use this scale to determine the score (10-100) that best represents the subject's activity status at the requested time point.

Karnofsky Scale (subject age > 16 years)	Lansky Scale (subject age <16 years)
Able to carry on normal activity; no special care is needed	Able to carry on normal activity; no special care is needed
100 Normal, no complaints, no evidence of disease	100 Fully active
90 Able to carry on normal activity	90 Minor restriction in physically strenuous play
80 Normal activity with effort	80 Restricted in strenuous play, tires more easily, otherwise active
Unable to work, able to live at home cares for most personal needs, a varying amount of assistance is needed	Mild to moderate restriction
70 Cares for self, unable to carry on normal activity or to do active work	70 Both greater restrictions of, and less time spent in active play
60 Requires occasional assistance but is able to care for most needs	60 Ambulatory up to 50% of time, limited active play with assistance/supervision
50 Requires considerable assistance and frequent medical care	50 Considerable assistance required for any active play, fully able to engage in quiet play
Unable to care for self, requires equivalent of institutional or hospital care, disease may be progressing rapidly	Moderate to severe restriction
40 Disabled, requires special care and assistance	40 Able to initiate quite activities
30 Severely disabled, hospitalization indicated, although death not imminent	30 Needs considerable assistance for quiet activity
20 Very sick, hospitalization necessary	20 Limited to very passive activity initiated by others (e.g., TV)
10 Moribund, fatal process progressing rapidly	10 Completely disabled, not even passive play

Signature: \_\_\_\_\_ Date: \_\_\_\_\_ Time: \_\_\_\_\_

**DOTATOC PET-CT Case Evaluation Pre-Scan**

**Patient ID:** \_\_\_\_\_

**I. Indication of Ga-68 DOTATOC PET-CT (check one)**

- Initial staging of pathologically proven NET
- Restaging after completion of treatment to detect residual disease
- Suspected recurrence of previously treated NET
- Monitoring response during therapy of NET

**II. YOUR WORKING STAGE FOR THE PATIENT BEFORE Ga-68 DOTATOC PET-CT IS: (check one)**

- No evidence of disease / In remission
- Metastases in multiple sites
- Primary disease only / Local recurrence
- Metastases with unknown primary
- Liver metastases only
- Unknown or uncertain

**III. PRIOR TREATMENT**

Other previous therapy? (check ALL that apply)

- Surgery for primary tumor or metastasis
- Chemotherapy
- External beam radiotherapy
- Hepatic directed therapy (SIR-spheres, bland embolization, chemoembolization)
- PRRT (type \_\_\_\_\_)
- Octreotide / Lanreotide
- None

**IV. CURRENT TREATMENT**

- Octreotide LAR or Lanreotide
- m-TOR inhibitors (i.e. everolimus) or TK inhibitors (i.e. sunitinib)?
- Other chemotherapy \_\_\_\_\_
- Other treatment \_\_\_\_\_
- None

If on treatment, what is your current impression (before PET) of your patient's response to currently ongoing therapy? (check one)

- Clearly responding, but uncertain about degree of response
- Possible partial response, but uncertain about degree of response
- Suspect no response
- Suspect progressive disease

**V. MANAGEMENT / THERAPY**

If Ga-DOTATOC PET were not available, your current management strategy would be? (check all that apply)

- Observation (with close follow-up)
- Additional Imaging (CT, MRI) or other non-invasive diagnostic tests
- Tissue Biopsy (surgical, percutaneous, or endoscopic)
- Octreotide LAR
- Surgery for primary tumor / debulking surgery
- Liver directed therapy/Liver transplant
- PRRT
- Chemotherapy or Other Biologic Modifiers (m-TOR inhibitors and/or TK inhibitors)
- Palliative External Beam Radiation Therapy
- Other Supportive care

Signature: \_\_\_\_\_ Date: \_\_\_\_\_ Time: \_\_\_\_\_

**DOTATOC PET-CT Case Evaluation Post-Scan** Patient ID \_\_\_\_\_

**I. Compared to your Pre-PET assessment, your impression of overall extent of disease is?**

(choose only one)

- More extensive
- No change
- Less extensive

**II. Did the PET scan show evidence of cancer activity that was not previously documented?**

- Yes
- No

**III. Your Post-PET working clinical staging is: (select only one)**

- No evidence of disease / In remission
- Primary Disease only / Local Recurrence
- Liver metastases only
- Metastases in multiple sites
- Metastatic (distant) with unknown primary
- Unknown or uncertain

**IV. In light of the PET findings, which of the following management/treatment strategies are you now planning or have you already undertaken? (check all that apply)**

- Observation (with close follow-up)
- Additional Imaging (CT, MRI) or other non-invasive diagnostic tests
- Tissue Biopsy (surgical, percutaneous, or endoscopic)
- Octreotide LAR
- Surgery for primary tumor / debulking surgery
- Liver directed therapy/Liver transplant
- PRRT
- Chemotherapy or Other Biologic Modifiers (m-TOR inhibitors and/or TK inhibitors)
- Palliative External Beam Radiation Therapy
- Other Supportive care

Signature: \_\_\_\_\_ Date: \_\_\_\_\_ Time: \_\_\_\_\_

**V. Was there a change in management in light of the PET findings?**

- No Change
- Minor Change
- Major Change

Signature: \_\_\_\_\_ Date: \_\_\_\_\_ Time: \_\_\_\_\_

Patient ID: \_\_\_\_\_

## Ga-68 DOTATOC PET Adverse Event Questionnaire

Please only list AEs that are new and have happened since the Ga-PET scan.

POSSIBLE ADVERSE EVENTS	YES/NO	COMMENTS/NOTES
BODY AS A WHOLE		
Pain (abdominal)		
Pain (chest/breast)		
Pain (other/site)		
Fever		
Injection site reaction		
CARDIOVASCULAR SYSTEM		
Flushing (vasodilatation)		
DIGESTIVE SYSTEM		
Nausea		
Diarrhea		
Vomiting		
RESPIRATORY SYSTEM		
Dyspnea (shortness of breath)		
SKIN & APPENDAGES		
Rash		
Itching (pruritus)		
Hives (urticaria)		
Sweating		
Cyanosis (finger or toe discoloration)		
CENTRAL NERVOUS		
Visual disturbances		
Numbness of feet		
Numbness of fingers/hands		
Weakness of feet		
Weakness of fingers		
Burning sensation in feet		
Burning sensation in fingers		

Signature: \_\_\_\_\_ Date: \_\_\_\_\_ Time: \_\_\_\_\_

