## **Reporting Adverse Events or Unanticipated Problems Involving Risk to Subjects or Others**

### **Adverse Event Terminology**

#### **Adverse Event**

1. An AE is "any untoward medical occurrence in a patient or clinical investigation subject administered a pharmaceutical product and which does not necessarily have a causal relationship with this treatment". An adverse event can therefore be any unfavorable and unintended sign (including an abnormal laboratory finding), symptom, or disease temporally associated with the use of a medicinal (investigational) product, whether or not considered related to the medicinal (investigational) product. AEs include any of the following:

- Subject deterioration due to the primary illness at the onset of the trial
- Intercurrent illnesses
- Drug interactions
- Events related or possibly related to concomitant medications
- Abnormal laboratory values or changes of vital signs, as well as significant shifts from baseline within the range of normal, considered to be clinically significant by the Investigator.

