### **Not Related**

Exposure to study drug has not occurred; administration of study drug and the adverse event are not reasonably related in time; or the AE is considered by the Investigator to be due to a pre-existing condition, a known manifestation of the target disease, a recurrent condition, or is likely explained by environmental or diagnostic therapeutic factors or was preexisting and did not deteriorate.

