### **Possibly Related**

The AE occurred during or within a reasonable period of time after administration of the study drug, or a pre-existing event worsened within an appropriate period of time after administration of study drug, but the AE could be explained equally well by factors or causes other than exposure to the study drug. This category will also be used if there is a lack of information, or insufficient or conflicting evidence exists for classifying the causality of the AE.

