### **Probably Related**

The AE occurred during or within a reasonable period of time after administration of the study drug or a pre-existing event worsened within an appropriate period of time after administration of study drug, and at least one of the following criteria is applicable:

- the event could not be explained by the clinical condition or history of the subject, environmental or toxic factors, or other diagnostic or therapeutic measures;
- the event was an expected ADR associated with study treatment or a class-labeled drug effect;
- the AE subsided or disappeared after withdrawal or dose reduction of study treatment; or
- the AE recurred after re-exposure to study treatment.

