## **Adverse Event Recording and Reporting**

### **1. Adverse Event Recording**

At baseline, all SAEs and study-related AEs since signing of the Informed Consent Form will be recorded. After initial study drug administration, all AEs will be recorded. Each AE occurring to a subject, either spontaneously revealed by the subject or observed by the Investigator, whether believed by the Investigator to be related or unrelated to the study drug, must be recorded on the AE Case Report Form and on the subject's file. Subjects will report the type and severity of AEs without being given a list of fixed symptoms beforehand. The Investigator will determine the relationship of any AE to study drug (causality) and record it on the appropriate section of the AE CRF as well as the start date of the event, event grade, and whether or not the event meets one or more of the definitions of an SAE. Clinically significant changes in vital signs (e.g., tachycardia) or other clinically significant changes observed by the physician will be entered in the appropriate CRF.

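### The Appendix II adverse event questionnaire asks only for new events, so worsening of a pre-existing symptom after the scan may be missed

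*Combined protocol and SAP*

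**What the plan says.** The Ga-68 DOTATOC PET Adverse Event Questionnaire (Appendix II) opens with the instruction "Please only list AEs that are new and have happened since the Ga-PET scan". Below it is a list of symptoms, among them flushing, diarrhea and several kinds of pain, each with a yes/no box and a space for comments. There is no column for the state before injection and none for grade.

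Section III of the protocol treats change from an existing state as an adverse event:

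- The Adverse Event section includes "Subject deterioration due to the primary illness at the onset of the trial" and, for laboratory values and vital signs, "significant shifts from baseline within the range of normal, considered to be clinically significant by the Investigator".
- The Possibly Related category covers the case where "a pre-existing event worsened within an appropriate period of time after administration of study drug".
- The Probably Related category also names worsening of an existing event after dosing, provided that a further listed criterion is met.
- The Not Related category includes an event that was due to other listed causes "or was preexisting and did not deteriorate".
- The Adverse Event Recording section states: "After initial study drug administration, all AEs will be recorded".

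**The concern.** The definitions say that a worsened condition can be an adverse event, and even a drug-related one. The form's instruction, taken at its word, asks for something narrower. A patient who had flushing before the scan and has clearly more of it the next day has nothing new to list, although the protocol would have the worsening recorded and its cause assessed.

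The introduction notes that some neuroendocrine tumors secrete hormones in excess, and the form itself lists symptoms that a patient may already have on arrival. What is at stake is the completeness of the non-serious adverse event data reviewed under Appendix I. Under Table I there, an event judged possibly related is reportable to the Clinical Research Safety Officer at every grade, so a mild worsening left off the form could be a reportable event missed. The charging request in Section VIII names safety as one of the things that the study will test.

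**Working it through.** No arithmetic applies. The point depends on wording, so the check sets the definitions, the recording rules and the two collection forms side by side.

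1. **Is worsening an adverse event under the protocol?** Yes. Deterioration of the primary illness is listed outright. Two of the three causality categories name a pre-existing event that worsened, and the third names a pre-existing event only where it did not get worse. The categories make sense only if worsened events reach the investigator.

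2. **When are adverse events collected?** The Study Withdrawal/Discontinuation section gives two times: the end of the scan, about 90 minutes after injection, and a call at 18-36 hours. Table 1 marks the same two points for the first scan and repeats them for an optional second scan.

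3. **Which form serves each time?**

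| Time | Source | Limited to new events? |
|---|---|---|
| Injection to end of scan | Scan-day form, item 5, with a narrative field | No |
| Next-day contact, as described in the protocol text | Investigational Radiopharmaceutical Administration section | No |
| After the scan | Appendix II questionnaire | Yes |

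   The documents do not say at which contact the questionnaire is used. It asks about the time since the scan, and no other form in Appendix II is worded for that period, so its use at the 18-36 h contact is a reasonable inference.

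4. **Could worsening be recovered from other data?** Not readily. Table 1 marks no adverse event collection at Visit 1. The recording section limits baseline recording to serious and study-related events since consent. Screening procedures may take place up to 60 days before dosing. The examination page of the imaging-visit form goes by body system and carries no graded symptom list. Without a pre-injection state to compare with, the questionnaire could not show worsening even if it asked for it.

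5. **Can the number of affected events be worked out?** No. It would need the share of subjects with a listed symptom before injection, the share of those who worsen, and the share of worsenings missed by every other route. The documents give none of the three.

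6. **Does it touch the primary analysis?** No. The endpoint is change in management, taken from the pre-scan and post-scan forms. The 37% null, the 49% alternative and the 180 evaluable patients do not depend on adverse event data.

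**The case against.** The strongest reply is that the questionnaire does not govern recording. The recording section does, and it requires every event, volunteered or observed, to go on the adverse event case report form with start date, grade, causality and seriousness. The questionnaire has no fields for these and sits among forms labelled as samples, so it may be only a prompt sheet. The next-day contact is described broadly, the scan-day form is open, and the questionnaire has a comments column.

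Most of this stands, and it limits the point. A reader might infer that worsened symptoms are certainly lost. The documents do not support that: worsening up to the end of the scan has an open field, and staff who follow the recording section would write down later worsening too. What does not follow is that the wording is harmless. A prompt sheet decides what is asked and mentioned, and this one points away from worsening.

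A second reply is that a worsening after the scan is itself a new adverse event, so the instruction already includes it. That reading is possible but strained, because it makes the second half of the instruction, about having happened since the scan, redundant. At best the wording is ambiguous, and people completing the form may then apply it differently.

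A third reply is that little is expected: the protocol describes the peptide amount as too small for physiological effect and foresees no adverse events. That bears on how often the gap would matter, not on whether the form agrees with the definitions.

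**Conclusion.** The point holds in a limited form. The questionnaire's instruction is narrower than the protocol's definition of an adverse event and its rule for recording. Followed literally, it may miss worsening of a pre-existing symptom after the scan visit. This rests on two assumptions: that the form is used at the 18-36 h contact, and that its wording shapes what is reported there. The conflict between the texts is clear; its practical size is unknown.

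Three stronger readings are not supported:

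- A reader might assume symptom and worsening rates and set the result against the low risk bands in Appendix I. No such rates are in the documents, and the monitoring text supplied there is for Risk Level 4.
- A reader might infer that reports to the FDA are biased. Serious events go straight into a separate report whether or not they are related, and the expedited FDA notices concern serious, unexpected, associated events. The questionnaire does not restrict those routes.
- A reader might take the introduction to mean that many patients arrive with these symptoms. It says only that some tumors secrete hormones and others do not.

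This should be corrected, but it is a matter of safety data capture only.

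**What to change.** Change the questionnaire's instruction to: *List events that are new, or worse than before the injection, since the injection.* Add a pre-injection column to the same sheet, completed on the scan day before dosing and again before any second scan, so that worsening can be judged. The scan-day form needs no change of wording.

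Two details need care. The new wording starts at injection and so overlaps the scan-day form for about 90 minutes; the start date on the adverse event case report form, with the scan-day narrative, should be used to avoid counting one event twice. Also, the recording section says "Subjects will report the type and severity of AEs without being given a list of fixed symptoms beforehand", and going through a symptom list before injection sits awkwardly with that. Either fill the column from open questions or amend that sentence.

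The cost is a form revision, a brief symptom check before injection, and a few more recorded events, mostly disease symptoms.
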